2.1.3 Exploratory Objectives

- (1) **Objective:** To assess the effect of treatment with odanacatib 50 mg once weekly on total body BMD compared to placebo.

- (2) **Objective:** To assess the effect of treatment with odanacatib 50 mg once weekly on risk of morphometric vertebral fractures and on distal forearm BMD, compared to placebo, in patients who are bisphosphonate-intolerant (i.e. patients with a contraindication or a history of intolerance to bisphosphonates, or those considered by their physician to be unsuitable for bisphosphonate treatment).

- (3) **Objective:** To assess the safety and tolerability of treatment with odanacatib 50 mg once weekly, compared to placebo, in patients who are bisphosphonate-intolerant (i.e. patients with a contraindication or a history of intolerance to bisphosphonates, or those considered by their physician to be unsuitable for bisphosphonate treatment).

Product: MK-0822

9

Protocol/Amendment No.: 018-04

- (4) **Objective:** To assess the effect of treatment with odanacatib 50 mg once weekly on skeletal microarchitecture as assessed by quantitative 2-D histomorphometry and 3-D μ -CT on transilial bone biopsy specimens compared to placebo.
- (5) **Objective:** To assess the effect of treatment with odanacatib 50 mg once weekly on the incidence of major atherosclerotic cardiovascular events compared to placebo.
- (6) **Objective:** To estimate the treatment effect with odanacatib 50 mg once weekly at 3 years on the incidence of each of the fracture categories (vertebral, hip and non-vertebral).
- (7) **Objective:** To determine if baseline protein expression levels (as determined by proteomics) can predict response to treatment with odanacatib 50 mg once weekly on the risk of hip and/or vertebral fracture and/or increase in BMD of the hip and spine.
- (8) **Objective:** To determine if change-from-baseline protein expression levels (as determined by proteomics) (< 12 months) can predict long-term response to treatment with odanacatib 50 mg once weekly on the risk of hip and/or vertebral fracture and/or increase in BMD of the hip and spine.
- (9) **Objective:** To assess the effect of treatment with odanacatib 50 mg once weekly on the risk of hip, vertebral, and/or non-vertebral fractures compared to placebo as a function of genotype.

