The primary technology used for these measurements will be the Affymetrix Genome-Wide Human SNP Array Version 6.0™ and DMET Plus™ microarrays. The Genome-Wide Array measures, "906,600 SNPs and more than 946,000 probes for the detection of copy number variation." The DMET Plus array assays "markers in all FDA-validated genes, and covers more than 90 percent of the current ADME Core markers as defined by the PharmaADME group." These arrays were developed in collaboration with key scientific leaders from both industry and academia, per the manufacturer's website [30]. In addition, Solexa-type sequencing may be subsequently used to add greater resolution to the array-based data, thereby corroborating and confirming the genotyping findings, if any. Additional descriptions and details on sequencing can be found in [31].

The data generated in this study will be analyzed using a systems biology approach that considers the SNP, the underlying causal genes, and ultimately the association of the target genes to their downstream counterparts. Knowledge of polymorphisms that affect the expression of genes within bone and other tissues will be key to accomplishing this goal. The Kyoto Encyclopedia of Genes and Genomes (KEGG) pathways, gene ontology (GO) terms and genetic networks constructed from F2 mouse crosses will also help to define downstream counterparts for the data set. This analysis does not call for a strict candidate gene approach, because doing so would require all loci of interest to be defined *ad hoc*, and doing so would artificially minimize the available data set.

At the conclusion of this current study, the SPONSOR hopes to have found a set of polymorphisms that can be utilized in subsequent studies to a) enrich for patients more likely to respond to odanacatib 50 mg once weekly and b) identify patients at increased risk for fractures, etc. who would benefit from treatment. If successful, the aforementioned systems biology approach may facilitate an increased understanding of the genetic factors that underlie differences in bone mineral density, fracture, and treatment response to odanacatib. The SPONSOR will ensure that the samples analyzed in this study are put to the best use possible, and will be treated with the utmost respect for the protection of patient privacy. All applicable local and national laws will be followed with regard to data dissemination to patients upon request.

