The purpose of the proposed genetic analyses will be to identify those genetic markers or genotypes that associate with osteoporotic end points within two frameworks: (1) treatment with odanacatib and (2) treatment with placebo. Each consenting patient's genetic material will be genotyped to determine if specific genes are shared by all patients who display a progression of the disease, and/or a reverse based upon intervention. The specific goals are three-fold. First, to identify novel genes that are causal drivers of osteoporosis and can be used as potential targets for future intervention; second, to identify loci that predict disease and disease course; and third, to identify genes/proteins that can be utilized as biomarkers in downstream musculoskeletal studies to reflect a patient's likelihood to respond favorably to odanacatib. Identification of genetic markers that associate with musculoskeletal disease, e.g., osteoporosis, will be achieved by using both the biased approach of drug-metabolizing genes and unbiased genome wide scans. The primary analysis will be cross-sectional using the baseline clinical traits, while the secondary analysis will be longitudinal, using multiple regression models across all patients, in each of the two study arms separately, treating the genotypes as the independent variables and the phenotypes being the dependant variables. New composite measures of musculoskeletal disease, e.g., osteoporosis, are envisioned to be developed that combine multiple measures of bone and muscle health, e.g., BMD, LBM, bone quality, muscle quality, circulating protein markers, and genotype) and utilizes this new composite measure in both the cross-sectional case control studies as well as the longitudinal studies described above. Although a particular composite measure has not been chosen as of yet, one potential method of combining data is shown below. For example, a regression analysis can be conducted by simply treating the three measures (BMD, bone formation markers and bone quality [by biopsy or advanced imaging modality]) as elements of the mixed effect model, similar to the way repeated measures are dealt with, and such model can directly test if genotype is associated with any of these measures singly or through composite crossed terms of these measures. Given the evolving nature of the statistical methodology on GWAS, and biological understanding of musculoskeletal disease, any changes to the statistical methodology and analyses would be outlined and documented in the results memorandum.

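### The separate-arm genetic regressions do not test whether genotype changes the odanacatib effect, so for exploratory objectives 9 and 10 and the third genetic goal a purely prognostic marker can be mistaken for a response marker

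*Protocol*

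**What the plan says.** Protocol section 2.1.3, exploratory objective 9, is to assess the effect of odanacatib "on the risk of hip, vertebral, and/or non-vertebral fractures compared to placebo as a function of genotype". Objective 10 asks the same for BMD, height, safety, drug exposure and circulating bone markers. Objective 11 is a separate question: the effect of genotype itself on fracture risk.

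Section 3.5.5.1, under Genetic Markers, states the purpose as finding markers that "associate with osteoporotic end points within two frameworks: (1) treatment with odanacatib and (2) treatment with placebo". It lists three goals. The first two concern genes that drive osteoporosis and loci that predict disease and its course. The third is markers "to reflect a patient's likelihood to respond favorably to odanacatib".

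Two analyses are given:
- "The primary analysis will be cross-sectional using the baseline clinical traits".
- "the secondary analysis will be longitudinal, using multiple regression models across all patients, in each of the two study arms separately", with genotype as the predictor and phenotype as the outcome.

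Section 3.1.6 gives the intended use of the polymorphisms found; one use is to "enrich for patients more likely to respond to odanacatib 50 mg once weekly" in later studies.

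**The concern.** Objectives 9 and 10 and the third goal are effect-modification questions: does the odanacatib-placebo difference depend on genotype? A regression of phenotype on genotype within one arm has a different null, namely that genotype is unrelated to outcome in that arm. A gene that shifts BMD change or fracture risk by the same amount in both arms modifies nothing, yet it is a true positive for the odanacatib-arm regression. The baseline analysis involves no treatment, so it cannot separate the two cases. The crossed terms in the composite-measure example are crosses of outcome measures, not of genotype with treatment.

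At stake is the interpretation of the hits. If prognostic markers are carried into later trials as a means of selecting responders, those trials would select patients by risk, not by benefit from the drug.

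**Working it through.** The protocol gives no sample size, threshold or power for the genetic work, so there is no planned figure to reproduce. What follows is an illustration.

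**From the protocol.** SD of BMD percent change 4% (section 3.5.5.4); 906,600 SNPs on the array (section 3.1.6); equal allocation (section 3.5.1).

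**Assumed.** Allele frequency p = 0.3 with additive coding, so genotype variance is 2 × 0.3 × 0.7 = 0.42; 4,000 genotyped per arm; per-allele effect b identical in both arms, so the true interaction is zero; two-sided tests. Thresholds are nominal 5%, as for a short list of candidate SNPs, and 0.05/906,600 = 5.5e-8 for the full array. The protocol sets neither.

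**Formulas.** Non-centrality of the within-arm test: λ = b × √(0.42 × n)/4. Chance of significance in one arm: P = Φ(λ − c), ignoring the negligible opposite tail, where c is 1.96 at 5% and 5.43 at 5.5e-8. Chance of significance on odanacatib but not on placebo: P(1 − P). The interaction test rejects at its own level, because its null is true.

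**Worked case.** For b = 0.2 and n = 4,000, √(0.42 × 4,000) = 40.99.
- λ = 0.2 × 40.99/4 = 2.05.
- P = Φ(2.05 − 1.96) = 0.54.
- P(1 − P) = 0.54 × 0.46 = 0.25.

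| Threshold | b (% BMD per allele) | λ | Significant on odanacatib | On odanacatib, not placebo | Interaction test |
|---|---|---|---|---|---|
| 5% | 0.2 | 2.05 | 54% | 25% | 5% |
| 5.5e-8 | 0.2 | 2.05 | 0.04% | 0.04% | 5.5e-8 |
| 5.5e-8 | 0.5 | 5.12 | 38% | 24% | 5.5e-8 |

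A direct simulation with drawn genotypes (1,000 per arm, b = 0.25, 4,000 runs) gave 23.6%, 17.8% and 4.7%. The formulas give 24.9%, 18.7% and 5%.

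**Comparing significance between arms.** P(1 − P) is largest at P = 0.5, where it equals 0.25. A rule of significant in one arm and not in the other is therefore not a test of the difference between slopes.

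**When the drug cancels a gene's effect.** Take a placebo slope of 0.3 and an odanacatib slope of 0, with 4,000 per arm and 5% level.
- Placebo fit: λ = 0.3 × 40.99/4 = 3.07, power Φ(3.07 − 1.96) = 87%.
- Odanacatib fit: rejects at 5%.
- Difference of slopes: its standard error is √2 times larger, so λ = 3.07/√2 = 2.17 and power is about 58%.

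The gene is visible in the planned placebo fit. What is missing is a test that labels it a modifier.

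**The case against.** **Part of the plan fits its aims.** The within-arm framework is the stated purpose. The first two goals and objective 11 are prognostic, and the baseline and separate-arm fits serve them. This stands, and it confines the point to objectives 9 and 10 and the third goal.

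**No declaration rule.** A reader might infer that prognostic markers will be declared response markers. The protocol does not say so: it gives no null, threshold or rule for calling a marker a response marker, and the rule of significant on odanacatib but not on placebo is not in the text. Only *can be mistaken for* is supported.

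**Masked modifiers are not lost.** A reader might also infer that a gene whose effect the drug cancels would go unnoticed. The placebo-arm fit makes that too strong. The two slopes and their standard errors also suffice to test the difference, so the separate fits need not be discarded.

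**Nominal 5% does not suit a genome-wide scan.** This stands. At 5.5e-8, the 0.2% effect is flagged on odanacatib in about 0.04% instead of 54%. The error persists there only for larger effects.

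**The work is optional and exploratory.** Genetic sampling needs separate consent, the analyses are described as possible, and section 3.5.5.1 lets methods change with documentation in a results memorandum. This lowers the weight. It does not correct the method that is stated, which leaves three aims without a matching test.

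**Conclusion.** The mismatch is real but narrow. For exploratory objectives 9 and 10 and the third genetic goal, the stated analyses test association with outcome within an arm, or at baseline, and not whether genotype changes the odanacatib-placebo difference. I found no interaction term or between-arm contrast for genotype elsewhere in the protocol.

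The size depends on allele frequency, effect size, number genotyped and threshold, none of which the protocol fixes. For candidate SNPs at 5%, a purely prognostic marker of modest effect can be significant on odanacatib about half the time, and discordant between arms in up to a quarter. At a genome-wide level the problem is confined to larger effects. No primary or secondary endpoint is touched, so this is a minor point.

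**What to change.** In section 3.5.5.1, for objectives 9 and 10 and the third goal only, specify one model over both arms with treatment, genotype and genotype-by-treatment, plus stratum and region. Its form can follow the main analyses: Cox for clinical fractures, complementary log-log for morphometric vertebral fractures, and the longitudinal model for BMD and bone markers. Testing the difference of the two within-arm slopes is an equivalent route.

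State that any response-marker claim rests on that term, and give the multiplicity threshold for it. The threshold matters: interaction tests at nominal 5% over 906,600 SNPs would give about 0.05 × 906,600 = 45,330 false hits if none were a modifier.

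Keep the baseline and within-arm fits for the first two goals, objective 11 and description.

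The cost is a sentence or two and one model term, with no new data. The downside is fewer hits and lower power, since the difference of slopes has a standard error √2 times that of a single-arm slope.

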Tier 2 events include: Any clinical AE, serious clinical AEs, drug-related clinical AEs, and AEs leading to discontinuation of study medication, if their incidence is at least 1% in either of the treatment groups.

The same categories (any events, related events, serious events, discontinuations and events with incidence $\geq 1\%$) will also be considered Tier 2 for laboratory events

In addition, specific dental disorders, specific skin disorders and specific respiratory disorders with incidence $\geq 1\%$ will be handled as Tier 2. Furthermore, hypocalcemia (including decreased blood calcium) will also be considered Tier 2 events.

Product: MK-0822

56

Protocol/Amendment No.: 018-04

A predefined subset of the Merck-MedDRA dictionary determined before unblinding the data for the DMC interim analyses will be used to identify skin, dental, and respiratory adverse. This list will be updated regularly by the clinical team in a blinded fashion to account for MedDRA dictionary updates.

Specific dental disorders, specific skin disorders, specific respiratory disorders, and specific AEs with >0% incidence (irrespective of the incidence) will be tabulated as Tier 3 events.

The threshold of at least 4 events was chosen because the 95% CI for the between-group difference in percent incidence will always include zero when treatment groups of equal size each have less than 4 events and thus would add little to the interpretation of potentially meaningful differences. Because many 95% CIs may be provided without adjustment for multiplicity, the confidence intervals should be regarded as a helpful descriptive measure to be used in review, not a formal method for assessing the statistical significance of the between-group differences in AEs and predefined limits of change. For Tier 1 events, estimates of the difference in proportions of patients will be provided, along with the 95% confidence intervals and a formal test for the between-group differences using Miettinen and Nurminen method, taking the differential observation period per patient into account [23]. For Tier 2 events the same summaries and confidence intervals will be provided, but no formal statistical testing. For Tier 3 events, estimates within each treatment group will be provided.

- Serious adverse experiences and patients withdrawn due to an adverse experience will be listed. Adverse experiences occurring before the first intake of study medication will be listed in the appendix of the report for disclosure. In addition, a listing will be provided in the appendix of the report of all occurrences of overdoses (ingesting 2 or more tablets of blinded study therapy on the same day or within a 5-day period).

In addition to the above mentioned summary tables, time to first event will also be summarized graphically by a Kaplan-Meier curve for any adverse experience, drug-related adverse experiences, serious adverse experiences, adverse experiences leading to early treatment discontinuation, deaths, and for any skin adverse experiences. Similar graphs will be provided for laboratory adverse experiences. For patients who did not experience an adverse experience of the specific category (any, related, serious, leading to discontinuation) before that time, the time to event will be censored at the cut-off date, or at the last contact date for patients who discontinued early from the trial before the cut-off date.

The main adverse experience tables (Tier 1 and 2 adverse experience summaries of Table 3-11) will also be provided, restricted to patients who are (oral) bisphosphonate-intolerant. Similar adverse experience summary tables will be provided for upper gastrointestinal adverse experiences, for patients who are (oral) bisphosphonate-intolerant.

Product: MK-0822

57

Protocol/Amendment No.: 018-04

Table 3-11

Analysis Strategy for Safety Parameters

Safety Tier	Safety Endpoint [†]	p-Value	95% CI for Treatment Comparison	Descriptive Statistics
Tier 1	Skin AEs reported as ECI [¶]	X	X	X
	Serious respiratory infections confirmed by adjudication [¶]	X	X	X
	Any osteonecrosis of the jaw confirmed by adjudication [¶]	X	X	X
	Any morphea/scleroderma confirmed by adjudication [¶]	X	X	X
	Any delayed fracture unions confirmed by adjudication [¶]	X	X	X
Tier 2	Any AE Any Serious AE Any drug-related AE Discontinuation due to AE		X X X X	X X X X
	Specific AEs [‡] , Specific dental disorders, Specific skin disorders, Specific respiratory disorders (incidence ≥1% patients in one of the treatment groups), hypocalcemia PDLCs [‡] for lab tests (incidence ≥1% patients in one of the treatment groups)		X X	X X
Tier 3	Specific AEs [‡] , specific dental disorders, specific skin disorders, specific respiratory disorders, PDLCs [‡] for lab tests (incidence > 0 patients in one of the treatment groups)			X
	Change from Baseline Results (Labs, Vital Signs)			X
[†] AE references refer to both Clinical and Laboratory AEs. [‡] Includes only those endpoints not pre-specified as Tier 1 endpoints. [¶] Only considered as Tier 1 if the incidence is ≥ 4 patients in one of the treatment groups, otherwise they will be considered Tier 3. Note: PDLC=Pre-Defined Limit of Change.; X = results will be provided.				

Change from baseline at each of the on-treatment time points in vital signs and laboratory safety endpoints will be summarized for both treatment groups. The number (%) of patients with laboratory values outside predefined limits of change will also be summarized similarly (with confidence intervals on the treatment difference). More detail is in Appendix 6.7.

Product: MK-0822

58

Protocol/Amendment No.: 018-04

Qualitative Abnormalities on Bone Biopsies

The 2-D Histomorphometry and 3-D μ CT transilial bone biopsy measurements at Month 24 or the end of the study will be summarized as efficacy endpoints. The principle purpose of the histomorphometry and bone biopsies is to rule out an increased incidence of qualitative abnormalities (e.g. excessive osteoid, woven bone, mineralization defect, marrow fibrosis), the number (percent) of patients with a qualitative abnormality will therefore be summarized for both treatment groups, along with the Miettinen and Nurminen method [6] based 95% confidence interval on the difference in percentage. The incidence of qualitative abnormalities on the bone biopsies will be considered a safety endpoint in stead of an efficacy endpoint as described in the protocol.

3.5.5.3 Multiplicity

Several multiplicities are present in this study: multiple primary endpoints, multiple secondary endpoints, interim analyses. This section describes how the multiplicities for the final analysis will be handled. Multiplicity adjustment in the interims will be described in Section 3.5.5.6.

The study is planned to terminate and the final analysis will be performed when all pre-specified fracture endpoints have occurred. In addition, the DMC will review both efficacy (in the formal efficacy interims) and safety and can recommend early termination for either efficacy or safety, before all pre-specified events are seen, as described below.

Multiplicity Due to Multiple Primary Endpoints

This study is primarily designed to investigate the effect of odanacatib on morphometric vertebral, non-vertebral and hip fractures. To control the false positive error rate due to multiple fracture endpoints in the final analysis, a combination of a step-down closed-testing and Hochberg procedure [8] will be applied. First a step-down procedure will be utilized with the following order of clinical importance: (1) morphometric vertebral fractures, (2) hip and non-vertebral fractures.

This means that significance for hip and non-vertebral fractures can only be declared if there was also a statistically significant result for the morphometric vertebral fractures. If there is no statistical significance for morphometric vertebral fractures, no significant conclusions will be drawn from this study for any of the other primary endpoints.

To control the false positive error rate for multiple tests for hip and non-vertebral fractures, a Hochberg procedure [8] will be used. Under Hochberg procedure, p-values for treatment comparisons (for hip and non-vertebral fractures) will be ranked from the largest to the smallest (i.e. $P_1 > P_2$). If both p-values for hip and non-vertebral fractures are $\leq \alpha$, both corresponding tests will be considered significant and the testing stops. If however, the largest p-value is $> \alpha$, it is considered not significant and the other fracture endpoint will be tested at a $\alpha/2$ significance level.

Product: MK-0822

59

Protocol/Amendment No.: 018-04

A graphical presentation of the multiplicity adjustment strategy is in Figure 3-1 (Section 3.5.5.6).

In the interim analyses, the trial will not be terminated unless strong evidence (significance) is seen for all 3 primary fracture endpoints, more detail is provided below.

Multiplicity Adjustment for Secondary Endpoints

Secondary efficacy endpoints include clinical vertebral fractures, stature, BMD measures at different sites, and biochemical markers of bone resorption. Statistical significance for the secondary endpoints will only be considered if the treatment difference for the first primary endpoint (morphometric vertebral fractures) was significant. It is recognized that this does not account for the presence of multiple primary endpoints, but it is felt that this approach is clinically meaningful and acceptable.

For the purpose of addressing the issue of multiplicity due to multiple secondary endpoints, BMD measurements at the total hip, femoral neck, trochanter, lumbar spine, and distal forearm will be considered one family. Biochemical markers of bone resorption (s-CTX, u-NTx) will be considered a second family and clinical vertebral fractures and stature a third family. Within each family a Hochberg [8] multiplicity adjustment procedure will be used to ensure a family-wise type I error rate of 5% within each of the families (conditional on significance at later time points for BMD and height and conditional on significance at earlier time points for biomarkers). No adjustment for multiplicity across the families will be applied.

For BMD and height, a step-down procedure will be used to account for the multiplicity over time, starting from the last time point to the earliest time point where no significant conclusion can be claimed. At earlier time points significance will only be claimed if there was significance at the later time points and if from the Hochberg procedure including all other endpoints significance can be concluded, as explained in [24]. Since the very last timepoint in the study may be obtained only for a limited number of patients, the last timepoint which was performed for at least 50% of the patients will be taken as the last time point in this multiplicity adjustment strategy and the later time point(s) will be considered exploratory.

For biomarkers, a similar approach will be taken, starting from the earliest time point to the last time point where significance is claimed. This approach for biomarkers is taken because the treatment difference is not expected to increase over time after the first on-treatment time point (Month 6), while for BMD and height it is expected to increase.

Significance of the analyses of BMD endpoints in the subgroup of (oral) bisphosphonate intolerant patients will only be tested if the test for the same BMD endpoint in the full FAS population is significant after Hochberg adjustment procedure.

Product: MK-0822

60

Protocol/Amendment No.: 018-04

Alpha Adjustment for Interim Analyses

A DMC will monitor the safety of the patients in the study on a regular basis and will review efficacy in the formal efficacy interims. Before the first formal efficacy interim analysis, the DMC will mainly review safety and the study should not be terminated early for efficacy. To limit the effect of the interim analyses in this time frame on the final alpha level, a low alpha level will be used based on the same spending function used for the formal efficacy interim analyses. From the first formal efficacy interim onwards, the DMC will review both efficacy and safety and may recommend early termination of the trial both for efficacy or for safety. An alpha-spending function approach [25] will be used to handle the multiple looks due to these interim analyses. Details on the actual alpha levels are in Section 3.5.5.6.

